**MECHANISMS AND PHENOTYPES OF
HYPERTENSION IN PATIENTS IN
CHRONIC HEMODIALYSIS**

NCT06764277

DATE: 09/11/2025

STUDY PROTOCOL

 SALUD SECRETARÍA DE SALUD	Instituto Nacional de Ciencias Médicas y Nutrición Salvador Zubirán	 INSTITUTO NACIONAL DE CIENCIAS MÉDICAS Y NUTRICIÓN SALVADOR ZUBIRÁN	

Title				
Mechanisms and Phenotypes of Hypertension in Patients in Chronic Hemodialysis				
Number				
Clinical Trials.gov protocol NCT06764277.				
Investigation type				
Observational transversal studies of mechanisms, markers (diagnostic/predictive) and prevalence of phenotypes in patients in chronic hemodialysis Population (one) 1 (categorized by severity of hypertension in 3 groups: normotensive, prehypertensive, hypertensive) Study: Prospective, observational, unicentric, Open				
Investigators				
INVESTIGATOR	Institutional position	Role in the project	Telephone (ext.)	Correo-E
[name] [name]	Staff member, Dept of Nephrology and Mineral Metabolism	Principal Investigator		[contact]
[name] [name]	Staff member, Dept of Nephrology and Mineral Metabolism	Investigator	[name]	[contact]
Dra. [name]	Staff member, Dept of Nephrology and Mineral Metabolism	Investigator	[name]	[contact]
[name] [name]	Staff member, Dept of Nephrology and Mineral Metabolism	Investigator	[name]	[contact]
Dra. [name]	Bioimpedance Dpt.	Investigator	[name]	[contact]
Note. 2 new co-investigators added: [name] (Nephrology resident) and [name] (nephrology resident)				
Investigators experience and role in the investigation				
Investigator	Previous research experience			
[name] [name]	Research experience in nephrology and hypertension			
[name] [name]	Research Experience in nephrology and renal replacement therapy			
Dra. [name]	Research Experience in nephrology and renal replacement therapy			
[name] [name]	Nephrology resident			

Dra. [name]	Research experience in bioimpedance
Institution	
Instituto Nacional de Ciencias Médicas y Nutrición Salvador Zubirán.	Approved the project Yes (protocol NMM 4512-23-24-1)
Sponsorships of other institutions	
No _____	
Payment to investigators (other than employment in the institution)	
No .	
Abstract/Summary	

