
Title: Mechanisms and Phenotypes of Hypertension in Patients in Chronic Hemodialysis
 
Justification. Cardiovascular complications associated to arterial hypertension are critical determinants of the mortality of patients in chronic hemodialysis. Identification of the activity of the renin-angiotensin system and immune reactivity in association with water overload is of clinical importance because they are potentially treatable.
 
Aims. To examine systemic arterial blood pressure ambulatory blood pressure monitoring (ABPM) in the interdialytic period and its relation to the activity of the renin angiotensin system, immune reactivity and interdialytic weight gain in patients in chronic hemodialysis.
 
General design. Prospective study of a cohort of patients in the chronic hemodialysis program in the Instituto Nacional de Ciencias Médicas y Nutrición Salvador Zubirán. Patients with the inclusion criteria will be evaluated with ABPM during the 24 hours in the interdialytic period. Weight, blood pressure, dialysis characteristics will be recorded. Blood samples will be obtained for hormonal determinations and immune reactivity at the end of the interdialytic period. Ultrasound will be used for determination of cardiac output and central venous pressure. Systemic vascular resistance will be calculated. Electric bioimpedance will be obtained would be obtained the first post dialysis day of the long interdialytic interval. *
	

 • Note: bioimpedance was not obtained and was not part of the study 	
Background.	

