
Chronic kidney disease (CKD) is associated with arterial hypertension (AHT). AHT is more frequent in renal vascular disease, diabetic nephropathy and polycystic kidney disease ¹, the incidence of AHT in end stage CKD (eGFR<10ml/min/1.73m²) of any etiology is over 90% ². In CKD patients the etiology of AHT is multifactorial and sodium retention and volume expansion ^{3,4}, overactivity of the renin angiotensin system ⁵, proinflammatory immune reactivity ⁶⁻⁹, endothelin system ^{10,11}, the sympathetic nervous system¹², secondary hyperparathyroidism¹³, reduced kallikrein/kinin ¹⁴ and endothelial cell dysfunction and nitric oxide reduction¹⁵, are known to play a role.
 
In the patient with end stage CKD, the most important prohypertensive factor is sodium and water retention with extracellular volume expansion that results in increase in cardiac output and peripheral vascular resistance¹⁶. For this reason, the universally accepted therapeutic measure is to attempt to keep in the so-called dry weight ¹⁷. The determination of “dry weight” is controversial and in addition to absence of clinical signs of vascular congestion,
 
bioimpedance determinations have been used to estimate subclinical overhydration but its use has been associated with higher risk of dialysis hypotension and clinical determination of the lowest weight that is not associated with postural and dialysis hypotension or cramps and malnutrition ^{18,19,20}.
 
With the emphasis placed in overhydration as a cause of AHT in end stage CKD, not enough attention has been placed to other factors which may play an important role especially because there is no predictable correlation between the severity of overhydration and the severity of hypertension, patients with normal blood pressure have significant overhydration and patients with bioimpedance-determined dry weight may
	

have significant hypertension. It is our rough estimate that in 85-90% of patients in chronic hemodialysis hypertension is associated to volume overload without predictable correlation and 10-15% of the patients have normal blood pressure despite various degrees of water overload.

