Ambulatory blood pressure monitoring will be done with Space Lab ambulatory monitor (SpaceLabs Co) with cuffs appropriate for the patient's size starting after dialysis. Measurement will be programmed to be taken every 30 minutes during the day and every hour when the patient goes to bed. The patient will bring the equipment to the hospital when he comes for the next dialysis.

Biometric Bioimpedance. It was impossible to coordinate bioimpedance determinations within one week of the studies and this part of the study was omitted.

Blood samples and laboratory determinations. Blood samples (10 ml) will be taken from the venous side of the vascular access before the beginning of dialysis (end of the interdialytic period) and allowed to coagulate at 2-4°C. Serum samples will be stored at -80°C until the time of assay. All determinations will be done in the research laboratory of the Dept. of Nephrology and Mineral Metabolism of the Instituto de Ciencias Medicas y Nutrición "Salvador Zubirán". Angiotensin II will be determined by ELISA (my BioSource Cat.# MBS703599); Norepinephrine by ELISA (ABCAM, Cat. # AB287789); Copeptin by ELISA (Biotechne/NovusBiological, Cat, # NBP2-69822), TNF α by ELISA (Human TNF-alpha Quantikine HS ELISA, R&D systems, Cat.# HSTA00E). All laboratory determinations will be done following the instructions of the commercial supplier. Peripheral white cell counts were used to calculate the NMLR (neutrophils + monocytes /lymphocytes ratio) inflammation index.

Informed Consent.

Presented separately

Medical Intervention

None. Is an observational study.

Sample size

All the patients in the chronic hemodialysis program of the INCMNSZ that meet the inclusion criteria will be invited to participate.

Inclusion criteria

- 18 years of age or older
- More than 3 months in chronic dialysis
- Stable clinical conditions with no evidence of infection or treatment changes in the previous month

- Signed informed consent to participate in the study.

Exclusion Criteria

- Previous nephrectomy
- Participation of the patient in another clinical trial requiring interventional treatment
- Patients with prosthesis and pacemakers
- Incapacity of placement of ABPM or insufficient valid recordings
- Incomplete collection of data
- Voluntary withdrawing of informed consent

Statistical Analysis. .

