Gaussian (normal) distribution will be evaluated with Kolmogorov-Smirnoff tests. Data will be expressed with mean and standard deviation or standard error of the mean and 95% confidence interval. Variables with not normal distribution will be expressed with median and interquartile range. Categorical variables will be expressed as frequencies and percentages. Comparisons between two groups with normal distribution will be done with t tests and between several groups with one way ANOVA with Tukey post-tests. Comparisons in groups that do not have a normal distribution will be done with Kruskal-Wallis tests. Correlations will be explored with Pearson (data with normal distribution) or Spearman (data with not normal distribution). Normality of log2 data distribution will be explored when obtained data do not fit with a normal distribution. Statistical calculations will be done with software STATA (Statistic Data Analysis version 14.1 or with Graphpad 10 program. Two-tail p values <0.05 will be considered significant.

Groups.

There is one population of patients and for the purpose of some analyses, patients will be categorized in 3 groups by their mean ambulatory systolic blood pressure (ABP-SBP) : 1. ABP-SBP <130 mmHg (normotensives); 2) ABP-SBP 130-139 mmHg (prehypertensives) and 3) ≥140 mmHg (hypertensives)

Mechanisms for assignation of treatments.

There will be no treatment assigned as part of the study

Recruitment potential

We aim to recruit all patients that meet the inclusion criteria. Our estimate is 40-45 patients from a total of 50-55 in the chronic hemodialysis program of the INCMNSZ.

Recruitment incentives.

There will be no incentives.

Therapy

There will be no therapy as part of the study. Treatment received by the patient will not be modified.

Retirement of participants

Premature retirement of a participant could occur at the patient's request or by the unexpected development of fever or adverse event during the study. Cause of retirement will be duly recorded

Samples, administration and monitoring of the study.

Samples will be used only for the purposes of the study. The study will be conducted or supervised by one of the investigators. Any adverse event will be immediately notified to the treatment physician.

Investigates will meet every month to discuss the progress of the study.

Methods of contacting the participants

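### The three blood pressure groups are cut on on-treatment ambulatory pressure, and antihypertensive treatment enters no group or analysis, so severity and drug control cannot be told apart

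*Protocol*

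**What the plan says.** - **Group rule.** Protocol, Groups: "1. ABP-SBP <130 mmHg (normotensives); 2) ABP-SBP 130-139 mmHg (prehypertensives", with 140 mmHg or more as the third group. Measured mean ambulatory systolic pressure is the only criterion. The Investigation type entry describes the population as "categorized by severity of hypertension in 3 groups: normotensive, prehypertensive, hypertensive".
- **Role of the groups.** Protocol, Groups: "There is one population of patients and for the purpose of some analyses, patients will be categorized in 3 groups". The Primary Outcome is a relationship between ambulatory pressure and weight gain, angiotensin II and inflammatory markers. The Protocol's Statistical Analysis section provides Pearson or Spearman correlations as well as group tests. The SAP lists group tests only.
- **Treatment during measurement.** Protocol, Therapy: "Treatment received by the patient will not be modified". The inclusion criteria require "Stable clinical conditions with no evidence of infection or treatment changes in the previous month". None of the six exclusion criteria concerns antihypertensive drugs.
- **Data recorded.** General design in the Abstract: "Weight, blood pressure, dialysis characteristics will be recorded". Drugs are not named there, and neither document enters them as a covariate, stratum or sensitivity analysis.
- **Motivating phenotype.** Background, as the investigators' rough estimate: "10-15% of the patients have normal blood pressure despite various degrees of water overload". The text does not say whether this means pressure on or off treatment.

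**The concern.** On-treatment pressure reflects two things at once: how severe the hypertension is and how well drugs control it. A patient on several drugs with a mean of 125 mmHg falls in the same group as a patient on none, yet only the second clearly shows the phenotype that the Background describes. The one-month stability criterion holds treatment constant within a patient but does not make patients comparable with each other.

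Two results are exposed. The lowest group, which serves as the reference, may be a mixture of unknown composition, so its marker levels cannot be read as those of people who resist hypertension. The primary ambulatory pressure-marker correlations use the same on-treatment pressure and are unadjusted, so treatment can distort them too.

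**Working it through.** The documents give no effect size, SD or power, so there is no planned figure to reproduce. The only documented numbers are the expected 40-45 patients (Recruitment potential) and the 10-15% estimate (Background). Everything else below is an assumption.

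**1. Group composition.** Expected patients with normal pressure: 40 × 0.10 = 4.0 up to 45 × 0.15 = 6.75. Suppose the 10-15% refers to untreated status and drugs bring a share c of the remaining patients below 130 mmHg. The treated-hypertensive share of the lowest group is c(N − n) / [n + c(N − n)]. With c = 10%:
- N = 40, n = 4.0: 3.6 / 7.6 = 47%.
- N = 45, n = 6.75: 3.825 / 10.575 = 36%.

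If the 10-15% already describes on-treatment pressure, this arithmetic does not apply.

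**2. Effect when drugs lower pressure only.** Assumed model: untreated systolic pressure with mean 150 and SD 18 (13% below 130); z is the standardised untreated pressure; drug count = round(1.8 + b·z + noise with SD 0.8), limited to 0-4, with b = 0.5 or 1.0; marker correlation 0.40 with untreated pressure. Observed pressure = untreated pressure minus a fixed amount per drug. Repeat runs agree to about 0.01.

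| Lowering per drug | Share below 130 | Of these, 130 or more untreated | Marker correlation (true 0.40) |
|---|---|---|---|
| 5 mmHg | 21-25% | about 39-46% | 0.38-0.39 |
| 8 mmHg | 33-36% | about 60-63% | 0.35-0.36 |
| 10 mmHg | 44-45% | about 70% | 0.30-0.34 |

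The marker difference between the 140-or-more and below-130 groups falls from 0.83-0.85 SD to 0.78-0.81, 0.73 and 0.65-0.69 SD respectively.

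**3. Effect when drugs also shift the marker.** Assumed: untreated mean 150, SD 20; true correlation 0.40; 50% or 90% of those at 130 or more treated; a drop of 10 or 20 mmHg; marker shift of −0.5, 0 or +0.5 SD. The correlation ranges from 0.27 to 0.43. The group difference ranges from 0.56 to 0.97 SD, against 0.81 SD with nobody treated. The bias can go in either direction.

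**4. Scale against precision.** The smallest correlation detectable with 80% power at two-sided 0.05 is tanh[(1.96 + 0.842)/√(N − 3)]. This is 0.43 for N = 40 and 0.41 for N = 45. A true 0.40 is already at the edge of what this cohort can detect.

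**5. What splitting by drug use gives.** In the step 2 model, 37-72% of patients whose untreated pressure is below 130 take at least one drug. Being below 130 on drugs therefore does not prove controlled hypertension. Untreated patients below 130 are about 4-8% of the cohort: 40 × 0.04 = 1.6 to 45 × 0.08 = 3.6, or roughly 1-4 patients.

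**6. What adjustment gives.** In the same model, adding back 10 mmHg per drug returns the correlation to 0.39-0.40, but this is circular because the data were generated with a fixed effect per drug. Partialling out drug count gives 0.35 (b = 0.5) or 0.28 (b = 1.0), because drug count itself tracks severity. Neither adjustment is neutral.

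**The case against.** The strongest reply is that this is an observational study that states openly that treatment is unchanged, and that the groups are a secondary device. Much of that stands, and it rules out four stronger readings a reader might infer.

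- *That the lack of a washout is a flaw.* It is not. Measuring patients on their usual treatment is a legitimate, declared design. The gap is that treatment is not carried into the analysis.
- *That the whole hypothesis rests on these groups.* The Protocol limits them to some analyses, the primary outcome is a relationship with ambulatory pressure, and the hypothesis also covers absent nocturnal dipping, which the groups do not define. They carry more weight in the SAP only because it lists nothing but group tests.
- *That every marker association is shrunk.* This holds only if drugs leave the markers alone. Step 3 shows movement both ways.
- *That most of the normotensive group would be mislabelled.* The high percentages in steps 1 and 2 treat the 10-15% as off-treatment. If it describes patients as treated, the simulated 21-45% below 130 conflicts with the Protocol's own figure and the mislabelled shares lose their anchor.

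It is also fair that the loss of correlation is modest at 5 or 8 mmHg per drug, and that prevalence of normotension is not a listed outcome. None of this answers the core point: under the stated rule, a treated patient below 130 mmHg is called normotensive, and nothing in the plan would reveal it.

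**Conclusion.** The point holds as a gap in group definition and analysis, not as a fault in leaving treatment alone. The groups mix severity with drug control, and the continuous ambulatory pressure-marker relationships are confounded by treatment in a direction the documents cannot settle.

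The size is unknown because the number treated is not given. With drug effects of 5-10 mmHg per drug and no effect on the marker, a true correlation of 0.40 falls to about 0.30-0.39. Allowing marker shifts of half an SD, under the separate assumptions of step 3, it ranges from 0.27 to 0.43. The firmer consequence is for interpretation: findings in the lowest group cannot be read as findings about normal pressure despite overload unless drug use is known. The study remains analysable and the remedy is small.

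**What to change.** With no change to any patient's care:

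1. Abstract from charts the number and class of antihypertensive drugs in use at the ambulatory monitoring session, and tabulate them by group.
2. Rename the three groups as on-treatment pressure strata.
3. Report the below-130 stratum in two parts: no antihypertensive drugs, and on antihypertensive drugs. Do not label the second part controlled hypertension (step 5).
4. Limit conclusions about normotension despite overload to the untreated patients, descriptively.
5. Add one sensitivity analysis of the primary relationships that accounts for treatment, beside the unadjusted result. A fixed increment per drug over a stated range (for example 5-15 mmHg) or a partial correlation on number of drugs would serve, with the limits shown in step 6 stated.
6. Mark these additions as post hoc if data are already collected. That seems likely: the stated study dates are April 2023 to June 2024, the documents are dated 2025, and bioimpedance is already reported as not obtained.

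**Cost.** Two chart-abstracted variables, relabelled tables and one extra analysis. The untreated below-130 group may contain only about 1-4 patients, any per-drug increment is an assumption, and 40-45 patients support very few covariates.

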# **MECHANISMS AND PHENOTYPES OF HYPERTENSION IN PATIENTS IN CHRONIC HEMODIALYSIS**

**NCT06764277**

**DATE: 09/11/2025**

**STATISTICAL ANALYSES**

### **Statistical analyses.**

All statistical analyses will be performed using GraphPad Prism version 10. The normality of data distributions was assessed using the Kolmogorov–Smirnov test. For comparisons between two groups, unpaired Student's t-tests will be applied when data followed a normal distribution, and the Mann–Whitney U test will be used for non-normally distributed data. For comparisons among more than two groups, one-way analysis of variance (ANOVA) will be performed for normally distributed data, followed by Tukey's post hoc test. When data did not meet normality assumptions, the Kruskal–Wallis test will be used, followed by Dunn's post hoc test for multiple comparisons.

For all analyses, two-tailed p-values  $< 0.05$  will be considered statistically significant. The assumptions underlying parametric tests (normality and homogeneity of variances) will be verified prior to analysis; if assumptions were not met, appropriate non-parametric alternatives will be used as described above.

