The purpose of the study is to evaluate factors that may importantly contribute to hypertension in chronic dialysis patients; in particular, the renin-angiotensin system (RAAS), the sympathetic nervous system and inflammatory immune reactivity. In relation to the RAAS, Neuman et al.²¹, found that basal levels of angiotensin II are higher in patients with CKD than in normal controls, but the reduction resulting from volume expansion is normal, indicating that physiologic responses are normal. We also know from the studies of Shalekamp et al.²² that the activation of the renin-angiotensin system in CKD is not uniform and there are patients with normal and patients with high renin activity. In relation to inflammatory reactivity generated by autoimmune mechanisms, studies of several groups including ourselves^{6,7,23,24} have established the inflammation in the arterial wall, in the central nervous system and in the kidney play an important pathogenic role by reducing vasodilatory responses that may be corrected with T regulatory cells²⁵, increasing the activity of the sympathetic nervous system²⁶⁻²⁸, inhibiting pressure natriuresis²⁹ and stimulating sodium reabsorption^{30,31}. If these findings are shown in dialysis patients it is possible that anti-inflammatory treatment could have anti-hypertensive effects as it has been shown in experimental models and in patients³².

An important aspect is the relationship between interdialytic weight gain and the phenotypes of arterial hypertension (sustained hypertension, diurnal and nocturnal hypertension, normal nocturnal dipping, non-dipping, exaggerated dipping and reverse dipping) that may be evaluated with ambulatory blood pressure monitoring (ABPM)³³ that are associated with worse prognosis^{34,35}. Of interest, there are significant differences between ABPM and pre and post-dialysis blood pressure that are worthy to examine. and there is a high incidence of non-dippers in patients with CKD³⁶ and in patients with inflammation³⁷⁻³⁹.

Hypothesis and research questions.

What is the relative importance of the renin-angiotensin system, the inflammatory immune reactivity and water overload in the interdialytic blood pressure in dialysis patients?

Working hypothesis: In patients in chronic dialysis the activity of the renin-angiotensin system and the inflammatory reactivity play a critical role in the severity of hypertension and in the absence of nocturnal dipping of blood pressure

Outcomes.

Primary Outcome :

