Determine the relationship of blood pressure determined by ambulatory monitoring (ABPM) in the interdialytic period and the interdialytic weight gain and the levels of angiotensin II and inflammatory markers in patients in chronic dialysis.

Secondary Outcomes:

- 1) Determine the relationship of other parameters relevant to blood pressure pathophysiology with interdialytic weight gain and blood pressure
- 2) Evaluate the relationship between interdialytic weight gain, and other variables under study with hemodynamic parameters (systemic vascular resistance and cardiac output).
- 3) Evaluate differences between ABPM and dialysis blood pressure.

Methods. .

General

- Design of the study: One cohort. Observational prospective study.
- Patients: Patients in the chronic hemodialysis program in the Instituto Nacional de Ciencias Médicas y Nutrición “Salvador Zubirán” that meet the inclusion criteria and sign informed consent
- Date. abril 2023– junio 2024

- Days and hemodialysis and hemodialysis prescription will not be modified in the study. .
- Ambulatory blood pressure monitoring will be started after dialysis when the patient will be fitted with the equipment for ambulatory blood pressure monitoring and receive the instructions for its use.
- Blood samples (10 ml) will be taken at the end of the interdialytic period, (prior to the next dialysis) for the biomarkers under study.
- 1-2 hours after the end of dialysis the determination of cardiac output and central venous pressure determinations for calculation of the peripheral vascular resistance will be done by experts with experience in ultrasound methodology.

Methods

Hemodynamic determinations. Cardiac output will be measured by experts with experience by transthoracic echocardiography using ultrasound equipment Siemens Acuson P500 with convex transducer of 2-5Mhz and lineal transducer of 7.5Mhz. Measurements will be done in the 4th intercostal space at the mid clavicular line. Cardiac output (systolic volume x heart frequency) will be determined by ultrasound doppler of the flow of the outlet of left ventricle and the aortic area.

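### Secondary Outcome 3 compares two blood pressure measurements in the same patients, but every difference test the SAP lists is for independent groups and no paired method is named.

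*SAP*

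**What the plan says.** Protocol, Secondary Outcomes, item 3: "Evaluate differences between ABPM and dialysis blood pressure". The protocol's background text indicates which readings are meant: "there are significant differences between ABPM and pre and post-dialysis blood pressure that are worthy to examine". On the design, the Groups section says: "There is one population of patients and for the purpose of some analyses, patients will be categorized in 3 groups".

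SAP, Statistical analyses: the two-group rule opens "For comparisons between two groups, unpaired" and names Student's t-test, with Mann–Whitney U for non-normal data. For more than two groups it names one-way ANOVA with Tukey, or Kruskal–Wallis with Dunn. On checks it says: "The assumptions underlying parametric tests (normality and homogeneity of variances) will be verified prior to analysis". If a check fails, the SAP sends the analyst back to the non-parametric tests already listed.

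Protocol, Statistical Analysis: "Comparisons between two groups with normal distribution will be done with t tests", without saying paired or unpaired. It adds one-way ANOVA with Tukey, Kruskal–Wallis for non-normal data, and Pearson or Spearman correlation. The Recruitment potential section gives the expected size: "Our estimate is 40-45 patients from a total of 50-55".

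**The concern.** ABPM and dialysis blood pressure are measured in the same people, so the two sets of readings are not independent samples. A test for independent groups ignores the within-patient correlation and uses the wrong standard error for the difference.

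The planned assumption check would not reveal this. It looks at normality and equality of variances, not independence, and its fallback tests make the same independence assumption.

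At stake is a false negative. If patients with high ambulatory pressure also tend to have high dialysis pressure, an independent-groups test gives p-values that are too large and intervals that are too wide. A real difference between the two methods could be reported as not significant. Recruitment is limited by a programme of 50-55 patients, so the lost power cannot be regained by enrolling more.

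**Working it through.** **1. The listed methods, classed by what they assume**

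| Method | Where | Suits paired readings? |
|---|---|---|
| Unpaired t-test | SAP | No |
| Mann–Whitney U | SAP | No |
| One-way ANOVA with Tukey | SAP and protocol | No |
| Kruskal–Wallis (with Dunn in the SAP) | SAP and protocol | No |
| t tests between two groups | Protocol | Not stated; the SAP specifies unpaired |
| Pearson or Spearman | Protocol | Measures association, not a difference |

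Neither document names a paired t-test, Wilcoxon signed-rank test, Friedman test, repeated-measures ANOVA, mixed model or Bland–Altman analysis.

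**2. Inputs for the size of the effect**

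The plan has no power calculation to reproduce. From the documents: n = 40-45 (42 used below) and two-sided alpha 0.05. Assumed: SDs s1 and s2 (20/20 or 15/25 mmHg), within-patient correlation r (0.3, 0.5, 0.7) and a true difference of 8 mmHg, varied in step 5.

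**3. Standard errors**

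- Unpaired: √((s1² + s2²)/n)
- Paired: SDd/√n, where SDd = √(s1² + s2² − 2·r·s1·s2)

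With SDs 20/20, n = 42 and r = 0.5, the unpaired SE is √(800/42) = 4.36. SDd = √(800 − 400) = 20, so the paired SE is 20/√42 = 3.09. The ratio is 4.36/3.09 = 1.41. Over r = 0.3, 0.5, 0.7:

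- SDs 20/20: SDd = 23.66, 20.00, 15.49; ratio = 1.20, 1.41, 1.83
- SDs 15/25: SDd = 25.00, 21.79, 18.03; ratio = √850/SDd = 1.17, 1.34, 1.62

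**4. Type I error and power**

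For equal SDs, the true null rejection rate of the unpaired test is approximately 2·(1 − Φ(1.96/√(1 − r))) = 1.9%, 0.6% and 0.03% at r = 0.3, 0.5, 0.7. The table gives simulated values for the unpaired t-test; paired power is from the noncentral t with noncentrality 8/(SDd/√42).

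| SDs | r | Unpaired type I error (nominal 5%) | Power unpaired | Power paired |
|---|---|---|---|---|
| 20/20 | 0.3 | about 2% | 43% | 57% |
| 20/20 | 0.5 | about 0.6% | 42% | 72% |
| 20/20 | 0.7 | under 0.1% | 40% | 90% |
| 15/25 | 0.3 | about 2.3% | 41% | 53% |
| 15/25 | 0.5 | about 1.0% | about 40% | 64% |
| 15/25 | 0.7 | about 0.2% | 38% | 80% |

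At r = 0.5 with SDs 20/20, going from n = 40 to n = 45 moves power from about 39% to 45% unpaired and from 69% to 75% paired.

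The other listed tests behave alike (simulation, n = 42, equal SDs, 8 mmHg, r = 0.3, 0.5, 0.7):

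- Mann–Whitney against Wilcoxon signed-rank: 41% vs 55%, 40% vs 70%, 38% vs 89%
- Three equally correlated readings with one shifted by 8 mmHg, one-way against repeated-measures ANOVA: 41% vs 60%, 37% vs 75%, 32% vs 93%

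**5. Varying the assumed difference (SDs 20/20, n = 42), power unpaired vs paired**

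- 4 mmHg: 7% vs 24% at r = 0.5
- 12 mmHg: 82% vs 89% at r = 0.3, about 85% vs 97% at r = 0.5, 91% vs over 99% at r = 0.7
- 16 mmHg: 98% vs 99% at r = 0.3, 99% vs over 99% at r = 0.5

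**The case against.** The strongest reply is that this is an omission rather than a wrong choice. In these documents, groups means the three ambulatory systolic categories, and for those the unpaired tests are correct. No sentence assigns an unpaired test to Secondary Outcome 3. The protocol's t tests could include a paired one. The outcome is worded as an evaluation, not a hypothesis test, and does not say which ABPM summary, blood pressure component or dialysis reading is compared. For differences of 12 to 16 mmHg the choice of test alters the conclusion much less, or hardly at all.

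Much of this stands. The SAP's sentence is right for its own purpose, and the harm is conditional on the listed tests being used for this outcome. The effect of the assumed difference is real, and the comparison is under-defined.

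It does not close the gap. The protocol words its t tests as between two groups, the SAP specifies unpaired, and even the generous reading leaves no paired option for non-normal data and no method for three readings. A purely descriptive report would still need a paired interval. Correlation does not help: two readings can correlate perfectly and still differ by a constant.

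**Conclusion.** The concern holds and should be fixed. A stated secondary outcome has no valid test in the plan, and using the SAP's listed tests for it would give wrong standard errors and p-values.

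For positive within-patient correlation the error is conservative: it costs power and widens intervals, and it does not create false positives. For an assumed 8 mmHg difference with both SDs 20 mmHg and 42 patients, the loss is about 14 percentage points of power at r = 0.3 (57 − 43), 30 at r = 0.5 (72 − 42) and 50 at r = 0.7 (90 − 40). It is smaller for large differences.

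Only the sample size and alpha come from the documents; the SDs, correlation and difference are assumptions. The direction of the error depends only on the correlation being positive. The estimated mean difference (for complete pairs), the primary outcome and the comparisons among the three ambulatory systolic categories are not affected.

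**What to change.** Add to the SAP, and align the protocol's Statistical Analysis section:

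> Secondary Outcome 3 is analysed on within-patient differences, separately for pre-dialysis and post-dialysis blood pressure versus ABPM, with a paired t-test (Wilcoxon signed-rank if the differences are non-normal) and a 95% CI for the mean difference. If all three readings are analysed together, a repeated-measures model is used.

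In the same place, state which ABPM summary (24-hour, day or night) and which component (systolic, diastolic) is compared with which dialysis reading. Normality should be checked on the differences, not on each set of readings. Keep the unpaired tests for comparisons between different patients, such as the three ambulatory systolic categories. Bland–Altman limits of agreement are an optional addition if agreement is of interest.

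The cost is two sentences plus the definition of the comparison. No new data, patients or visits are needed. If the outcome has already been analysed with an unpaired test, it can be rerun on the same pairs and the change reported.
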